As with most medical innovations, the uptake and integration for PGx testing are impacted by several factors including provider knowledge, clinical evidence, patient interest, and reimbursement.⁸ From our previous research, we have learned that most physicians have little knowledge of what PGx tests were available and for which drugs, the purpose of testing, and applicability of test results,⁹ (findings confirmed by other groups.^{10,11}) Although some PGx tests have been taken up relatively rapidly in clinical practice,¹² others have had limited or delayed uptake.¹³ In addition to limited knowledge about PGx testing, some providers may have very limited time during an office visit to discuss PGx testing.¹⁴

The pharmacy practice has greatly evolved, expanding from traditional roles of compounding and dispensation to provision of a range of clinical services including vaccinations, clinical testing (e.g., cholesterol, A1C, and glucose), and medication therapy management (MTM).^{15,16} With an estimated 55,000 community pharmacies in the U.S., these settings enable more convenient access to health services that were once limited to physicians' office¹⁷. It is estimated that 56% of all prescriptions are filled at chain pharmacies, 15% at independent pharmacies, and 20% through mail order.¹⁸ Several studies have demonstrated that pharmacists' direct involvement in patient care can reduce health costs and improve clinical outcomes¹⁹⁻²¹ and they are a trusted resource by patients^{22,23} While pharmacists have been involved in implementation of PGx testing in clinic-based or hospital settings, often as a liaison between the testing laboratory and provider,²⁴⁻²⁶ the feasibility and impact of community pharmacist-delivered PGx testing has not been explored in depth.^{35,43}

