and can read and write in English, and have a new or existing prescription (<1 year active) for a drug listed in Table 1 to be eligible to participate. Each pharmacy will identify existing patients eligible for testing through a query of their database for active prescriptions for the selected drugs. If more than 30 patients in a pharmacy are identified by the database search, we will ask pharmacists to contact patients with the newest prescriptions. Patients will be contacted by phone or in-person by the pharmacist to introduce the study. Interested patients will be asked to visit the pharmacy to learn more about testing, sign the consent form requested by the testing laboratory, and provide a DNA sample (buccal swab). Patients who have had PGx testing for one of the genes in Table 1 or had an MTM within the past 12 months will be ineligible. All women and minorities who meet the study inclusion criteria will be eligible to participate in the study. Based on our power calculations, we estimate that we would need to enroll 18 patients per cluster (360 total).

Patients who consent to testing based on their pharmacist's recommendation will be asked to provide a buccal swab for DNA extraction. Patient samples will be sent for testing to Pathway Genomics laboratory. Testing will be provided at no cost for participants. As the Pathway Genomics' clinical tests are currently available to any clinician, only the consent required by the testing lab will be required of the patient.

Patients in the control arms will be identified by each participating pharmacy; two controls will be identified per each participant in the PGx arms (2:1) and matched on drug, age and gender. Time on treatment, medication changes (dose/drug selection), and refill history (adherence) data will be collected along with demographic data and compared to patients in the PGx testing arms. Based on their pharmacy records, patients who have undergone MTM or PGx testing outside of the study will be excluded from the control arm.

Risk/Benefit Assessment. If patients decide to have pharmacogenetic testing, a buccal swab sample is required. There are no known risks to a buccal swab sample. The sample, or DNA extracted from the sample, will be sent to the laboratory and stored only for the time necessary laboratory regulations.

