- **[Baseline & Follow-up]** Several secondary clinical outcomes will be measured to assess overall impact of PGx testing during the follow-up survey including information-seeking about side effects of new drugs and medication adherence. To assess medication adherence, we will use a combination of survey tools and refill data from the pharmacies. Participants will be asked to complete the validated Beliefs about Medicines Questionnaire (BMQ)¹⁰⁴ and Voils medication adherence scale (<https://sites.duke.edu/corrinevoils/versions-of-scale/>). Higher concerns and lower necessity measured by the BMQ have been associated with poorer medication adherence.^{105,107} Although the MMA scale is generally the more accepted tool for self-reported adherence, the BMQ scores can be used as a covariate to determine reasons for non-adherence (e.g., poor satisfaction). In addition, we will assess the psychological impact of testing using the Multidimensional Impact of Cancer Risk Assessment (MICRA) questionnaire.¹⁰⁸ The total score on anxiety and distress subscales range 0 to 105 with a higher score indicating more distress. No studies have defined a cut-off value for high distress; therefore, we will follow the approach by Bjornslett et al¹⁰⁹, and define high distress as a MICRA score above the mean +1 standard deviation.

Pharmacist Patient Log. We will ask pharmacists to keep track of their interactions with each patient to enable analysis of feasibility of delivery of PGx testing in a pharmacy setting and compare responses between pharmacy and patient surveys (see Appendix 7). In particular, we will ask pharmacists to document reason for each interaction with a patient, time spent addressing interaction, whether by phone or in-person, the test result, time spent following up with patient's provider, whether any drug or dosing adjustments were made based on the test result, and refill data. Pharmacy adherence data will extend 6 months after test results are communicated. Two measures of adherence based on data from the pharmacy will be generated: 1) the proportion of days covered¹¹⁰⁻¹¹² (PDC; # of days with drug on-hand]/[# of days in the specified time interval] (x 100)]; and 2) medication possession ratio (MPR; # of days of

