medication supplied within the refill interval/# of days in refill interval). Patient-reported adherence data will be collected at baseline and 1 month following receipt of test results. The log record will be stored in a folder with the patient's name in the pharmacy; at the completion of the study, once the log record is returned to the research team, the log record will be coded and the folder will be destroyed so that the research team will have no patient identifier.

No identifying information will be collected on the patient logs. Forms will be kept in the pharmacy in a folder with the patient's name and any other relevant information noted by the pharmacist. At the completion of the study when the log is picked up by the research team, the folder will be discarded and all forms will be labeled with a study ID# number. A code will be established and accessible only to the clinical research coordinator and PI.

Pharmacist Surveys. Participating pharmacists will be asked to complete two surveys (Appendix 6). First, a baseline survey will be administered to all pharmacists prior to participation in the CE training. The baseline survey will assess knowledge of and experience with PGx testing, comfort with integrating PGx testing into pharmacy practice, comfort discussing PGx testing with patients, and experience with patient education and MTM. Pharmacist and pharmacy practice data will be collected including number of years in practice, other pharmacy services offered, and estimated time to complete each service. Second, we will administer a survey at the completion of the study to re-evaluate knowledge of PGx testing, comfort with integrating PGx testing into pharmacy practice, and comfort discussing PGx testing with patients. In addition, we will ask about the likelihood of adding PGx testing to their pharmacy services and major barriers to implementation including potential impact of adding this service on other currently offered services.

Table 2. Outline of proposed survey content for pharmacists and patients.

Pharmacists	Patients

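### PDC is built from the study pharmacy's own fills, so moving a prescription is scored as non-adherence and unequal leaving would bias the comparison with controls

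*Combined protocol and SAP*

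**What the plan says.** The [Baseline & Follow-up] item under Patient Surveys (Part III) says of adherence: "we will use a combination of survey tools and refill data from the pharmacies". Pharmacist Patient Log adds "Two measures of adherence based on data from the pharmacy will be generated" and fixes the period: "Pharmacy adherence data will extend 6 months after test results are communicated".

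- PDC is the number "of days with drug on-hand]/[# of days in the specified time interval", times 100.
- MPR is days of "medication supplied within the refill interval/# of days in refill interval". The refill interval is not defined.

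For controls, Patient Study Population (Part II) says "two controls will be identified per each participant in the PGx arms (2:1) and matched on drug, age and gender". It continues: "Time on treatment, medication changes (dose/drug selection), and refill history (adherence) data will be collected along with demographic data", and these are to be compared with the PGx testing arms. No index date, continued-use requirement or study contact is described for controls. Patient Surveys lists age, gender, co-medications and time on treatment for them, but no adherence questionnaire.

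The text mentions no claims data or other pharmacies' records and gives no rule for a prescription that moves. The background section reports "56% of all prescriptions are filled at chain pharmacies, 15% at independent pharmacies, and 20% through mail order".

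**The concern.** A fill made elsewhere is invisible to the study pharmacy. Over a fixed 6-month window, an adherent patient who moves a prescription therefore looks the same as one who stopped taking the drug.

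The design gives a reason to expect unequal leaving. Before the window opens, a tested patient has agreed to visit, had the requisition signed by the prescriber, given a sample, waited 7-10 days for the result and been reached to discuss it. Each step selects people still engaged with that pharmacy, and the MTM arm adds two sessions. Controls are matched on drug, age and gender only.

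Nothing else in the plan catches the error. Self-reported adherence stops 1 month after results and is timed to receipt of results, which controls do not have. The missing-data paragraph in Data Analysis is framed around comprehension and drop-out. A moved prescription is not missing data in that sense, because it enters PDC as days without drug.

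At stake is the Data Analysis hypothesis that testing improves adherence. Both randomised arms are tested, so the matched controls are the only concurrent untested comparator.

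**Working it through.** **Inputs from the documents.** 20 pharmacies × 18 patients = 360 tested, which agrees with the stated total. Two controls each gives 2 × 360 = 720. The window is 6 months, taken as 180 days. Part III says many of the medicines come in 90-day allotments; 30-day fills are tried as well. The plan states no PDC, MPR or leaving figure to reproduce.

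**Assumptions.** Leaving rates, a PDC standard deviation (SD) of 25 points, independent patients, fills starting on day 0, and leaving at a uniformly distributed time.

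**Step 1: one mover.** A fully adherent patient fills 30 days' supply on days 0 and 30, then goes elsewhere.

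- PDC = 60/180 = 33%.
- MPR over a fixed 180 days = 60/180 = 33%.
- MPR from first to last observed fill = 30/30 = 100%.

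PDC over the fixed window is wrong for this patient. MPR depends on a denominator that the plan does not define.

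**Step 2: average loss per fully adherent leaver.** Drug on hand outlasts the departure, so the loss depends on days' supply.

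- 90-day fills: PDC is 50% if leaving before day 90 and 100% after. Mean (50 + 100)/2 = 75%, a loss of 25 points.
- 30-day fills: PDC is 1/6, 2/6, …, 6/6 with equal probability. Mean (1+2+3+4+5+6)/36 = 21/36 = 58.3%, a loss of 41.7 points.

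**Step 3: false gap with no true effect.** Gap = excess leaving in controls × loss per leaver. Standard error (SE) = 25 × √(1/360 + 1/720) = 1.61 points.

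| Assumed excess leaving in controls | 90-day fills | 30-day fills |
|---|---|---|
| 0 points | 0 | 0 |
| 5 points | 1.25 (0.77 SE) | 2.1 (1.29 SE) |
| 10 points | 2.5 (1.55 SE) | 4.2 (2.58 SE) |
| 20 points | 5.0 (3.10 SE) | 8.3 (5.16 SE) |

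**Step 4: cross-check with imperfect adherence.** A 180-day refill simulation used equal true adherence in both groups (mean PDC about 84% with 30-day fills, 89% with 90-day fills).

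| Assumed leaving, tested v control | Spurious PDC gain (90-day to 30-day fills) | False-positive rate, two-sided 5% test |
|---|---|---|
| 5% v 15% | 2.2 to 3.6 points | 58% to 88% |
| 10% v 20% | 2.1 to 3.4 points | 49% to 78% |
| 20% v 10% | −2.1 to −3.4 points | not a gain: sign reversed |
| equal | 0 | 5% |

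The simulated SDs in the two 10-point-excess rows were about 15 to 22 points, below the 25 assumed in Step 3, so these error rates are higher than the SE multiples in Step 3 imply. For 5% v 10-20% leaving, fixed-window MPR shifted by 1.5 to 6.0 points. MPR between observed fills shifted by less than 0.3 points, slightly the other way.

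**The case against.** The strongest reply is that the bias needs unequal leaving and the documents give no leaving rate for any group. The background percentages are market shares, not transfer rates. Equal leaving produces no gap and reversed leaving reverses its sign. If adherence is tracked on the original drug, a switch prompted by the test could lower measured PDC in tested patients. All of this stands, and it limits what can be said about size and direction. It does not let the analyst tell leaving from stopping, or report how often leaving occurred.

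A reader might go further and infer any of the following, none of which the documents support:

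- **Both measures are necessarily distorted.** MPR between observed fills is practically unaffected.
- **Controls are taken whether or not they still use the pharmacy.** The text is silent on this; it does not say that continued use is ignored.
- **A leaver loses half the window on average.** That ignores drug on hand, and is twice the loss for the 90-day supplies the protocol mentions.
- **The trial will show a false gain.** That requires more leaving among controls, which is plausible but undocumented.

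The log form (Appendix 7) is not in the text available, so it may record transfers. The log contents listed in the body do not include them, and no log is described for controls.

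On reach, comprehension is the primary outcome. The randomised comparison is affected only if leaving differs between the arms, and there both arms also have self-report.

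**Conclusion.** The point holds for PDC. Computed as written over the 6 months after results, it scores an adherent patient who moves a prescription as non-adherent, and any difference in leaving between tested patients and controls becomes a false adherence difference. For an assumed 10-point excess of leaving in controls, the false gap is about 2.5 to 4.2 PDC points. That is 1.55 to 2.58 SE with 360 v 720 independent patients and an assumed SD of 25. These sizes illustrate the mechanism and do not forecast the result. The direction that favours the hypothesis is plausible from the recruitment steps but not established. For MPR the point is conditional on a fixed-window denominator.

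This concerns the adherence outcome, which Part III calls secondary but Aim 2 includes in the trial's primary goal. The primary comprehension endpoint is untouched. The gap should be closed before data collection ends: the named folders are to be destroyed when logs are collected, and dates of leaving are best gathered while pharmacies still hold them.

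**What to change.** 1. Give each control the index date of the matched participant's results. Apply the same pre-index activity requirement, a fill at the pharmacy before that date, to all groups. State the PDC interval and define the MPR refill interval.
2. Record any documented transfer-out, move, mail-order switch or death, with its date, in the same way in both testing arms and the controls. End the PDC denominator there, and the MPR denominator too if it is a fixed window, counting days on hand only up to that date.
3. Report the share leaving in each group.
4. Show PDC with and without this censoring as a sensitivity analysis. Do not restrict instead to patients with a fill late in the window: that selects on behaviour after the index date and removes patients who truly stopped.

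The cost is modest: a departure reason and date added to the record extraction, plus one further analysis. Pharmacy records may not capture every move or mail-order switch, and departures may be documented less fully for controls. The censored result should therefore be read alongside the leaving rates and not treated as fully corrected.

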Aim 2. To compare the effect of PGx testing offered as a stand-alone or as part of medication therapy management (MTM) with respect to patient, pharmacist, pharmacy setting variables. Using a cluster randomized study design, pharmacies will be randomized to provide PGx testing only or PGx testing with MTM. Study outcomes will be gathered through pharmacist and patient surveys and follow-up interviews with pharmacists. The primary goal of the clinical trial is to study the difference between the effects of these two services on patient acceptance, comprehension, satisfaction, and medication adherence; secondary outcomes include acceptance of recommendations for drug/dosing changes (AIM 2a). The second part of this aim will evaluate pharmacist and pharmacy variables relevant to the sustainability of these delivery models (AIM 2b).

[figure not shown]
- 2a) Patient perceptions are increasingly used to assess quality of care. We will compare and assess patients’ 1) satisfaction with testing experience in a pharmacy setting and perceived value of testing; 2) comprehension of test result; and 3) medication changes and adherence. We will collect demographic information that may be associated with patients’ satisfaction, comprehension and perceived value of PGx testing, such as age and education status as well as information about past experiences with prescribed medications. Data will be collected through a baseline and one follow-up survey. We hypothesize that patients overall will be satisfied with PGx testing provided through the community pharmacy, particularly those who have experienced adverse responses or a poor outcomes, are taking multiple medications, and are older. Furthermore, we hypothesize that patients’ increased awareness about their genetic risk to adverse responses will result in improved medication adherence and sharing of results with other providers. Patients with lower education status, chronic illnesses, and who are older may report greater benefit from PGx testing delivered as part of an MTM, with respect to comprehension and overall satisfaction. We will also assess whether patients’ perceived value or satisfaction was influenced by the presence/absence of PGx variants.

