Survey Data Analysis. Analysis of data collected from surveys will be conducted using a software package such as STATA. We will calculate frequency data and statistical associations for the respondent characteristics. Both univariate and multivariate analyses will be conducted for hypotheses (see below). Because the trial uses a cluster design, the analysis will use logistic mixed effects regressions by including treatments as the fixed effect of interest and clusters as random effect. We will first test if the random effect is significant or not. If not, then we will use regular logistic regression to perform the analysis; if significant, we will continue using mixed effect logistic model. In either case, odds ratios and 95% confidence intervals will be generated to assess strength of associations between treatments and outcomes. A secondary analysis will be performed in which the comprehension outcome is not collapsed into “correctly identifying the presence of any variant versus no variants”, but will include correctly indicating the result for each gene (e.g., slow/fast metabolism vs. average). In this case, a logistic random effects model will also be applied with pharmacist and patient as random effects. If a sufficient number of patients are enrolled per drug, a stratified data analysis by drug will be performed to detect any differences regarding comprehension, adherence, or satisfaction. In addition, the impact of time to treatment will be assessed on patient satisfaction and adherence.

- We hypothesize that patients will have a higher level of comprehension of test results from the MTM plus PGx testing than those receiving testing offered as a stand-alone service.
- We hypothesize that patients overall will be satisfied with PGx testing provided through the community pharmacy and likely to have testing again in this setting
- We hypothesize that patients will find PGx testing beneficial, particularly those who have experienced adverse responses or a poor drug outcome in the past, are taking multiple medications, and are older.
- We hypothesize that patients' increased awareness about their genetic risk to adverse responses will result in improved adherence through assurance about the effectiveness and/or safety of their medications.
- We hypothesize that the additional time required to deliver PGx testing as part of an MTM session may present a barrier to providing PGx testing through this approach.

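### No stated model fits the self-reported adherence score, use of its baseline value is not committed to, and in the MTM arm that baseline is taken after adherence has already been addressed

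*Combined protocol and SAP*

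**What the plan says.** All references are to the combined protocol and SAP.

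- **Role of adherence.** Study Objectives, Aim 2, makes it the primary goal to study the "difference between the effects of these two services on patient acceptance, comprehension, satisfaction, and medication adherence". Part III later groups adherence with the secondary clinical outcomes and names comprehension as the primary outcome.
- **Timing of the score.** Part III, Pharmacist Patient Log: "Patient-reported adherence data will be collected at baseline and 1 month following receipt of test results".
- **Model.** Data Analysis, Survey Data Analysis: "the analysis will use logistic mixed effects regressions by including treatments as the fixed effect of interest and clusters as random effect". Results are to be given as odds ratios. The pharmacy effect is tested first: "If not, then we will use regular logistic regression to perform the analysis".
- **Covariates.** The same paragraph promises multivariate as well as univariate analyses but lists no covariates. The only covariate named for adherence is the Beliefs about Medicines Questionnaire (BMQ), in Part III: "the BMQ scores can be used as a covariate to determine reasons for non-adherence".
- **When baseline is taken.** Table 2 and the Part III paragraph on the patient study population place the baseline survey after consent to testing. Part II, MTM Session #1, has the pharmacist record adherence barriers and recommendations during the session. Testing is reviewed, and consent to it sought, at the session's end.

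**The concern.** One of the adherence hypotheses is that adherence will improve, and each patient's starting score will be on file. Yet a reader cannot tell from the plan how the score will be analysed: as a 1-month value, as a change, adjusted for baseline, or cut into two categories to suit a logistic model. That choice would be made after the data are seen.

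Two things are at stake. The first is precision. With few pharmacies, the arms can differ by chance in starting adherence, and an analysis of the 1-month score alone passes that difference into the estimate. The second is validity. The natural remedy is to adjust for baseline, but under the present schedule the MTM-arm baseline follows the start of the intervention.

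**Working it through.** **The plan's own figure.** 20 pharmacies × 18 patients = 360, as stated. The power calculation behind it cannot be reproduced, because the effect size, power, ICC and dropout are not given.

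**Inputs.** From the documents: 20 pharmacies and 18 patients each. Inferred: 10 pharmacies per arm (from the threshold of 10 under Pharmacist Study Population) and two-sided 5% (from the 95% intervals). Assumed: ICC 0.01, 0.05 or 0.10; correlation ρ between baseline and 1-month scores of 0.3, 0.5 or 0.7; 80% power for the unadjusted 1-month score; both scores complete for all 18 patients.

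**Chance imbalance at baseline.** With a patient-level SD of 1, the variance of a pharmacy mean is v0 = ICC + (1 − ICC)/18, which is 0.065, 0.103 and 0.150 at the three ICCs. The SD of the difference between arm means is √(2·v0/10) = 0.11, 0.14 and 0.17 SD.

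**Effect of adjustment.** There are two bounding cases:

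- Baseline explains only within-pharmacy variation: v = ICC + (1 − ICC)(1 − ρ²)/18.
- Baseline explains both levels equally: v = (1 − ρ²)·v0.

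On a t test with 18 df, 80% power needs a noncentrality of 2.963. This is multiplied by √(v0/v). Example at ICC 0.05 and ρ = 0.5:

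- Within only: v = 0.05 + 0.95 × 0.75/18 = 0.0896; 2.963 × √(0.1028/0.0896) = 3.17; power 85.1%.
- Both levels: 2.963/√0.75 = 3.42; power 89.9%.

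| ρ | ICC 0.01 (within / both) | ICC 0.05 | ICC 0.10 |
|---|---|---|---|
| 0.3 | 83.0 / 83.6% | 81.8 / 83.6% | 81.2 / 83.6% |
| 0.5 | 88.4 / 89.9% | 85.1 / 89.9% | 83.3 / 89.9% |
| 0.7 | 95.5 / 97.5% | 89.9 / 97.5% | 86.5 / 97.5% |

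The gains over 80% are therefore about 1 to 4, 3 to 10 and 7 to 18 points.

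**Check with a fixed effect instead of a fixed starting power.** For 0.3 SD at ICC 0.05, same t test, power is 51% unadjusted. At ρ = 0.5 it is 56% (within only) to 63% (both levels).

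**Timing.** The order of events in the MTM + PGx arm is session #1 with adherence content, then review of testing, then consent, then baseline survey. In the PGx-only arm no MTM session precedes the survey. If session #1 shifts the reported baseline by b SD in one arm, an adjusted analysis subtracts roughly ρ × b from the arm difference. The documents give no basis for b.

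**The case against.** A reader might infer that the plan leaves only arm and pharmacy in the adherence model, and so ignores the patient's own baseline. The text does not support that. Treatment is called the fixed effect of interest, not the only one; multivariate analyses are planned; and the logistic model with odds ratios suits the dichotomous comprehension endpoint discussed next to it. No model is tied to the adherence scale at all. A hypothesis of improvement with two time points could equally mean a change score, which does use baseline. This part of the objection stands: the defect is lack of specification.

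It does not remove the point, because a baseline-adjusted model does at least as well as a change score. With equal variances at both times and equal correlation at both levels, the change score has variance 2(1 − ρ)·v0. At ρ = 0.5 that equals v0, so power is 80% against 90% adjusted. At ρ = 0.7 it is 95.1% against 97.5%, a gain of only 2.4 points.

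The objection is also right that the size rests on assumptions, that adjusting under the current schedule could bias the comparison, and that refill-based adherence and comprehension are untouched. There is no error in giving BMQ a covariate role.

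**Conclusion.** The point holds as a gap in specification, with a timing problem that must be settled before the usual remedy is safe. Adherence is a stated arm comparison, both scores are collected, and neither a model for the scale nor use of the baseline is laid down.

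The benefit of adjustment over the 1-month score alone ranges from about 1 to 18 points of power, depending wholly on the assumed ρ, ICC and 80% starting point. It is small if ρ is near 0.3, or if pharmacies differ a good deal and baseline does not explain that difference. The documents do not show that the trial will lose any particular amount of power. A reader might also take this as a weakness in the primary analysis. It is not: comprehension is measured at follow-up only. The change is a worthwhile improvement and does not threaten the trial's main conclusion.

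**What to change.** 1. **Data Analysis, Survey Data Analysis.** State that 1-month self-reported adherence is analysed by a linear mixed model with arm, the patient's baseline score on the same scale, and pharmacy as a random effect that is kept whatever its significance test shows. Report the unadjusted estimate alongside. Name the scale: the Part III text has patients complete the Voils scale, while Table 2 lists MMA.
2. **Part III, patient study population, and Table 2.** Have the baseline adherence survey completed before MTM session #1 in the MTM + PGx arm, and at the equivalent point before the testing discussion in the PGx-only arm. Without this step, the adjusted model should not be adopted.
3. **BMQ.** It can keep its stated covariate role.

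**Cost.** No new data item is needed, but this is more than a wording change to the analysis section, because survey timing is a small protocol change. Some patients will complete a baseline survey, with its $20 payment, and then decline testing. Survey consent is already taken on the survey's own welcome page, separately from consent to testing.
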